5.1 Study Population, Recruitment and Retention

- Target sample size: This will be a convenience sample of learners already scheduled to rotate with the palliative care team. There is an anticipated approximately 20 learners per group screened and hope to recruit about 15 per group
- Anticipated accrual rate: 60-75%
- Training site: Children's National Hospital
- Recruitment site: only those who rotate with the palliative care team at Children's National Hospital
- Restrictions to enrollment: none

- Participation will not be limited based on health, only that they need to be healthy enough to participate in the palliative care rotation for at least ½ day, as the target population is trainees
- Participants will be incentivized to participate in the focus group with a \$20 gift card to a location approved by the IRB to compensate them for their time

5.2 Inclusion Criteria

- Age: Must be an adult, greater than or equal to 18 years old
- Must have rotated with the pediatric palliative care team for at least ½ day during the study period
- Must speak English

5.3 Exclusion Criteria

- There are no exclusion criteria for this study

5.4 Vulnerable Subjects

The purpose of this study is to improve the training and educational process for trainees (students and other learners), who will already be taking part in the palliative care rotation.

Their status as a trainee within the program will not be negatively affected if they decide that they do not want to participate in the study, and they will not be pressured to participate in the study due to their status as a trainee.

5.5 Recruitment

The subject population will come from trainees who have rotated with the palliative care team during the study period. They will not be required to participate in the study to rotate with the team; however, they will be emailed rotation evaluation surveys soon after their rotation. On the first page of the evaluation survey, they can consent to participate in the study. If they participate in the study in the intervention group, they can indicate that they would be willing to participate in a focus group and will be sent a separate link (disconnected from their survey data) to indicate that interest. Subjects who indicate interest will be invited to participate in a focus group. The evaluations will be done using Redcap software to protect the privacy of the learners' responses. Any data that is downloaded for analysis will be de-identified and stored on password protected computers on the Children's National Hospital network. Only authorized study team members will have access to the data.

5.6 Retention

- All study subjects in the control group will only participate in the study for the extent of one survey
- Study subjects in the intervention group will participate in the study for the extent of one survey

- Subjects in the intervention group will then be recruited to possibly participate in a single focus group
- Participants will be incentivized to participate in the focus group with a \$20 gift card to a location approved by the IRB to compensate them for their time

5.7 End of Participation Criteria and Procedures

Participants are free to withdraw from participation in the study at any time upon request. Their participation in the study is only when they complete their evaluation form and if they choose to participate in the focus group. For those that require evaluations for their training programs, study participation does not affect their ability to participate successfully in a rotation with the palliative care team or receive positive evaluations, since the processes are independent.

Participants may also withdraw during the focus group.

Section 6: Study Procedures

6.1 Informed Consent/Assent and HIPAA Authorization

Informed consent is a process that is initiated prior to the individual agreeing to participate in the study. It continues throughout the individual's study participation. Because HIPAA-protected information will not be collected in this study, a Waiver of Consent Documentation will be requested, and an information sheet will be used to recruit participants.

- All study subjects will be adults who are fluent in English (as they are rotating with the palliative care team), so will provide their own informed consent
- When study subjects receive emails with their evaluation for the rotation, they will also be sent the information sheet attached to the email
- If they choose to participate in the study, they can indicate their agreement by clicking on the evaluation survey link that will be housed on the information sheet
- Subject privacy will be assured as there will be nothing linking their identity to their survey responses
- The evaluation form will be sent to all rotators. That email will also include an information sheet describing the study, and they will be able to decide whether to complete the form and whether to have their data contribute to the study at the point that they fill it out. The information sheet will be written, with no names attached, and it will be sent after their rotation is complete, and their evaluations are sent. They will have four weeks to complete the evaluation survey, so they are able to discuss it with others prior to agreeing to participate. All of this is to minimize any sense of obligation or coercion.
- The participants may withdraw their consent at any time throughout the course of the study.

- A copy of the information sheet will be given to the participants for their records via email
- The rights and welfare of the participants will be protected by emphasizing that the quality of their education will not be adversely affected if they decline to participate in this study. Additionally, they will be consenting post intervention, so they will be receiving education without bias from the faculty.
- Because names and email addresses will be collected for the focus group scheduling and not tied to participants' medical information, HIPAA Section is not applicable.

6.2 Screening Process

All trainees rotating with the palliative care team who are 18 years or older and participated in at least ½ day with the team clinically within the study period are eligible to participate. The program director and associate program director are the two key personnel in this study and have access to the contact information of the trainees. They will all be included and sent an evaluation form for the rotation within two weeks after the last date of their rotation. They choose whether to participate in the study before completing their evaluation form.

6.3 Study Interventions and Follow-Up

Database Development. Initial database development will be done in Microsoft Excel until June 2026. This database will include links to a variety of resources in the following categories, to be used alongside experiential and on-the-fly teaching: didactics (lectures by palliative care faculty, seminars from other sources, online lectures, videos, and podcasts), interactive resources (online modules, interactive websites, simulations), and written resources (books, articles, handouts, and websites or blogs). Topics covered will include palliative care symptom management, communication in different circumstances, diagnostic, prognostic and treatment information, decision making, ethics, active resources for patients and families, hospice, psychosocial and spiritual support of patients and families, end of life care, and well-being and self-care.

Every resource will be characterized based on questions answered in a learning self-assessment, when a trainee begins their rotation. It will ask about standard objectives and elective objectives, level of training, experience in hospice and palliative medicine, learning style, and time on service. Starting in July 2026, for each trainee in the intervention group, a curriculum will be built per their rotation specifications. Following the tailored curriculum, learners will be given an evaluation to evaluate how effective the rotation experience was at meeting the objectives.

Intervention Implementation. Between January – June 2026, the rotation education will continue as normal for the control group. Rotators will be sent an

introductory email with standard rotation goals and learning objectives and resources. They will share their individual learning objectives on the first day of the rotation. Preceptors will provide resources and clinical opportunities in an *ad hoc* manner for learning based on their individual learning objectives, as is the standard right now. Between July – December 2026, learners with the team will be asked to provide answers to the self-assessment approximately one month before the start of the rotation, and the flexible curriculum tool will be used to generate a tailored set of resources for them. Of note, some rotators organize their rotation on a shorter time frame, and for those learners, the self-assessment will be sent when they set up their rotation to be done as soon as possible.

The final evaluation survey will be sent within two weeks of the last day of their rotation. They will be given four weeks to complete the evaluation.

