3.4 Secondary Outcome Measure(s)

The secondary outcome measure is response to the question “I achieved my specific objectives for the rotation (which the learner provided at the start of the rotation).” It will be quantified using a Likert scale with five choices, 1-5, with 1 set to strongly disagree and 5 set to strongly agree.

Other outcome measures include whether (via Likert scale, scores ranging from Strongly Disagree to Strongly Agree as defined above):

- The learner was provided with a variety of resources to meet their learning objectives
- The education they received matched their level of training
- Their education was appropriate to their previous exposure to hospice and palliative medicine
- The education matched their learning style
- They felt the rotation was valuable

- The clinical educators promoted an open, respectful, and safe environment for discussion, learning, and improvement
- They would recommend this rotation to others

Open-ended feedback will be elicited regarding strengths of the rotation, areas for improvement, and practice changes, both on the survey and during the focus group.

Lastly, learners will be assessed on their confidence in meeting each standard rotation objective, on a Likert scale of 1-5, both before and after the rotation.

All of this allows the team to gather more information to understand why there was benefit for the flexible learning curriculum, if indeed there was one.

Section 4: Study Design

This is a single-center pilot study evaluating the use of a flexible curriculum tool to improve the experience of rotators with the palliative care team, measured by how well the rotation helps them meet standard as well as individualized learning objectives. It will not be blinded.

All learners will be sent a welcome email that will include a pre-rotation self-assessment, identifying type of learner and personal experience with palliative care, self-identified preferred ways of learning, length of time on the rotation, and personal learning goals.

All learners in the first half of the study period will be in the control group, and all learners in the second half of the study period will be in the intervention group. Outcomes will be measured on post-rotation evaluation surveys, one for each trainee, sent to them after their rotation is complete. Qualitative data will be more deeply interrogated with a focus group of trainees who participated in the intervention.

Section 5: Study Enrollment and Withdrawal

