6.4 Description of Study Procedures/Evaluations

The primary deviation from standard education is described above in intervention implementation. The behavioral intervention is the use of the flexible curriculum tool to systematically tailor rotation resources to each learner. It will be utilized by one of the study personnel who are also the program director and associate program director of the fellowship program and primarily responsible for coordinating rotator education. The tool will output the recommended resources for each learner, which will then be passed along. A description of the tool, as well as a standard operating procedure for its utilization, is attached.

Self-Evaluations: All learners will be sent a self-evaluation describing their level of training and palliative care experience, preferred learning styles, time on the rotation and personalized learning goals.

Rotation Evaluation: Following the rotation, all learners have an opportunity to evaluate the rotation. Individuals not participating in the study can access a separate QR code/link in the body of the first survey email sent to them to provide rotation feedback in RedCap system. The QR code is in the Panda Palliative Care Office on the door and is available for all learners to provide anonymous feedback to faculty. The evaluations are provided at the end of the year to faculty. As standard of practice for the rotation, the program/rotation site director sends an email at the end of the rotation to the trainees with the same QR code as a reminder to complete these evaluations. This information can be found in document called

For those participating in the survey, a separate evaluation process will be utilized. Similar to standard of practice, evaluations will be sent via email and submitted through a different RedCap Survey. It is called “Post Rotation Evaluation.”

The focus group will be organized once all intervention group participants have submitted their evaluations by the end of January 2027. It will take place in February to early March 2027 over Microsoft Teams teleconferencing software and will use the attached focus group guide, developed using best practices.¹¹

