8.4 Description of Statistical Methods

This study is a pre-/post-interventional study; however, different participants will receive the intervention than those that receive the control education because of the nature of the palliative care rotation. Essentially, for the first 6 months of the study period, rotators will receive the control education, and for the next 6

months of the study period, they will receive education using the intervention, the flexible education tool. All evaluations from each 6-month period will be aggregated to preserve anonymity, and there will be no learners who are in both groups.

Demographic data will be collected during the self-assessment and reported using descriptive statistics:

- Level of training (categorically in percentages)
- Amount of experience in hospice and palliative medicine (categorically in percentage)
- Learning style (categorically in percentages)
- Time on palliative care service (categorically in percentages)

For all outcome measures that use Likert scales (ordinal data), the sample size is so small that it is assumed data will not fall within a normal distribution, so a Mann-Whitney U test will be to analyze it and report z-test statistic and p-value, as well as the interquartile range. A p-value of 0.05 will be used for statistical significance.

Individual participant data will not be published.

Confidence ratings will be compared at pre-post time points for significant improvements within each group using a paired t-test. Overall improvement between control and intervention groups will be compared using a student's t-test to compare the change in confidence. A p-value of 0.05 will be used for statistical significance.

Qualitative data, including responses to open-ended survey questions and focus group data, as mentioned in 8.2, will be analyzed using inductive thematic analysis using DeDoose software.

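### As written, Section 6.3 elicits learners' individual objectives at different times and by different routes in the two groups, while Sections 4 and 6.4 give all learners the same form

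*Protocol*

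**What the plan says.** Section 6.3 treats the two periods differently.

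- **Control (January–June 2026).** Rotators receive an introductory email with the standard goals, objectives and resources. On individual objectives it says: "They will share their individual learning objectives on the first day of the rotation". No self-assessment is mentioned in this description.
- **Intervention (July–December 2026).** Here "learners with the team will be asked to provide answers to the self-assessment approximately one month before the start of the rotation". There is an exception for late bookings: "some rotators organize their rotation on a shorter time frame, and for those learners, the self-assessment will be sent when they set up their rotation".

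Other parts of the protocol describe the form differently.

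- Section 4: "All learners will be sent a welcome email that will include a pre-rotation self-assessment". Its listed contents include personal learning goals.
- Section 6.4: "All learners will be sent a self-evaluation describing their level of training and palliative care experience, preferred learning styles, time on the rotation and personalized" (the quote stops before its final item, the learner's own goals). No timing is given.
- Section 6.3, under database development: "Every resource will be characterized based on questions answered in a learning self-assessment, when a trainee begins their rotation". This is a different timing from the month's lead given later in the same section.

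Two uses of this information matter for the analysis. The secondary outcome item in Section 3.4 reads "I achieved my specific objectives for the rotation (which the learner provided at the start of the rotation". Section 8.4 says: "Demographic data will be collected during the self-assessment and reported using descriptive statistics". Section 3.4 also has confidence rated on a 1–5 scale before and after the rotation for each standard objective, without naming a day or a form for the earlier rating.

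**The concern.** The secondary outcome is a rating against a yardstick that learners set for themselves. Objectives written on a structured form weeks ahead may differ in number, ambition and specificity from objectives told to a preceptor on arrival, after reading the standard goals. If the way of setting them differs by group, a difference in the ratings could reflect the yardstick as well as the tool.

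The comparison is already sequential and non-randomised, so a procedural difference that coincides exactly with group cannot be separated from the intervention in the analysis. The four demographic variables in 8.4 (level of training, experience in the field, learning style, time on service) are the only listed descriptors for judging whether the groups are alike. If controls do not complete the form, the protocol names no other source for them.

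**Working it through.** The protocol states no power, effect size or standard deviation, so there is no figure to reproduce. The check is a comparison of passages.

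**1. Who completes the form?** Sections 4 and 6.4: all learners. Section 6.3, in its account of the two periods: mentioned for intervention learners only. The first two cannot be squared with a literal reading of the third.

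**2. When?**

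| Place | Control | Intervention |
|---|---|---|
| Section 4 | before the rotation, no lead time given | same |
| Section 6.3, database development | at the beginning of the rotation | same |
| Section 6.3, implementation | form not mentioned; objectives shared on day one | about one month ahead, later for late bookings |
| Section 6.4 | no timing | no timing |

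There are three descriptions of timing, and only the implementation paragraph separates the groups.

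**3. Which objectives does the secondary outcome refer to?** The item points to objectives given when the rotation starts. That fits the control timing in 6.3. It does not fit a form completed about a month earlier. The outcome is a single post-rotation rating with nothing subtracted, so what may differ is the reference objectives, not a baseline score.

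**4. Where do the control demographics come from?** Section 8.4 names the self-assessment. Under Sections 4 and 6.4 controls have it. Under 6.3 read literally they do not. The source is therefore unclear, not shown to be absent.

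**5. When is pre-rotation confidence rated?** Section 3.4 says only that it is before the rotation. The contents of the self-assessment listed in Sections 4, 6.3 and 6.4 do not include a confidence rating; the nearest is the remark in 6.3 that the form asks about standard objectives. Section 5.6 limits participation to one survey per subject, which does not settle where an earlier rating would sit. Unequal confidence baselines are possible, but no passage establishes them.

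**6. Can a size be attached?** Only by assumption. Suppose timing alone moved the mean confidence change by d standard deviations of the change, with no true effect. The planned two-sample t-test then has noncentrality d/√(2/n). With the 10 to 15 per group of Section 8.5 and two-sided α = 0.05:

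| n per group | d = 0.25 | d = 0.5 |
|---|---|---|
| 10 | 0.25/0.447 = 0.56; rejects 8.3% | 0.5/0.447 = 1.12; rejects 18.5% |
| 15 | 0.25/0.365 = 0.68; rejects 10.1% | 0.5/0.365 = 1.37; rejects 26.2% |

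The values of d are not in the protocol. The table shows how sensitive the test would be to a shift, and is no evidence that one exists. It does not apply to the secondary outcome, where no change score is formed.

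**The case against.** **Section 6.3 describes teaching, not data collection.** Its introductory email may be the welcome email of Section 4, and telling preceptors one's goals on day one does not rule out having completed the form. This is a fair reading, and it is why the finding is an unresolved contradiction and not a proven omission. It does not close the gap: even then, no lead time is fixed for controls, and nothing says whether the written or the spoken objectives are the reference for the rating.

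**Early elicitation is part of the intervention.** The tool needs answers in advance, whereas controls receive usual practice. This stands in part. But Section 6.4 defines the intervention as use of the tool, and controls can complete the same form without receiving the tool's output. The late-booking exception also means that the month's lead is not uniform within the intervention group.

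**The stakes are modest.** This is an openly sequential pilot that accepts it may be underpowered, and the primary outcome uses standard objectives supplied to every learner. That stands, and it limits the weight of the point.

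**Stronger readings to avoid.** A reader might infer that the confidence change is measured from different baselines in the two groups, that an earlier baseline would read lower and favour the tool, or that controls have no demographic data at all. The protocol supports none of these. The earlier confidence rating has no stated time or form in either group, nothing indicates a direction, and Sections 4 and 6.4 do give controls the form.

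**Conclusion.** The point holds as an inconsistency in procedure that should be corrected. If 6.3 is followed, the reference objectives for the secondary outcome are set at different times and by different routes in the two groups, the intervention timing departs from the outcome's own wording, and the control source for the 8.4 demographics is in doubt. This rests on 6.3 being the section that staff follow; if Sections 4 and 6.4 govern, what remains is the missing common lead time and the mismatch in wording.

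For confidence, the supportable statement is that the time and form of the earlier rating are not given, so unequal baselines cannot be excluded. No size or direction of bias can be stated for either outcome. The primary outcome is unaffected.

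**What to change.** - Reword 6.3 so that control and intervention learners complete the same self-assessment form at the same stated lead time, with the same rule for late bookings. Bring Section 4, Section 6.4 and the database paragraph of 6.3 into line with it.
- Record the earlier confidence rating on that form, before any tailored resources are sent. A day-one rating would be less safe, because the protocol does not say when resources reach the learner and they could arrive before then.
- Make the written objectives on the form the reference for the secondary outcome in both groups, and change the item's wording in Section 3.4 and the Protocol Summary to say so.
- The control period began in January 2026 and the latest revision is dated 02/11/2026, so some controls may already have rotated. For them, report how many completed the form and when. A true pre-rotation record cannot be recovered later.

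The cost is a paragraph in 6.3, small edits elsewhere and use of a form that the plan already has. The downside is that controls write down their goals ahead of the rotation, a slight change from usual practice that Sections 4 and 6.4 already state. How the earlier and later confidence ratings are paired is a separate matter that this change does not settle.
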